6.2 Death

All-cause mortality will be considered for the primary analysis. All-cause mortality includes all deaths, regardless of whether the cause of death is determined.

For the secondary analysis, death will be classified in two primary categories, cardiovascular or non-cardiovascular.

- Cardiovascular death is defined as death due to atherosclerotic coronary heart disease, cerebrovascular accident or (complication of) peripheral embolization, and includes deaths due to acute MI, stroke, sudden death, non-sudden death, unwitnessed death, and procedure-related deaths.

- Non cardiovascular death includes deaths due to all other causes.

All deaths will be assumed cardiovascular in nature unless a non-cardiovascular cause can be clearly shown, with the exception of death without any additional information, which will be classified as unknown cause of death.

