6.4 Bleeding Classification

All bleeding events will be considered in patients undergoing cardiac and non cardiac surgery.

Bleeding events will be classified according to BARC classification.

Bleeding Academic Research Consortium Definition for Bleeding (Ref 43)

- Type 0: no bleeding
- Type 1: bleeding that is not actionable and does not cause the patient to seek unscheduled performance of studies, hospitalization, or treatment by a healthcare professional; may include episodes leading to self-discontinuation of medical therapy by the patient without consulting a healthcare professional

- Type 2: any overt, actionable sign of hemorrhage (eg, more bleeding than would be expected for a clinical circumstance, including bleeding found by imaging alone) that does not fit the criteria for type 3, 4, or 5 but does meet at least one of the following criteria: (1) requiring nonsurgical, medical intervention by a healthcare professional, (2) leading to hospitalization or increased level of care, or (3) prompting evaluation

- Type 3

Type 3a: overt bleeding plus hemoglobin drop of 3 to <5 g/dL* (provided hemoglobin drop is related to bleed); any transfusion with overt bleeding

Type 3b: overt bleeding plus hemoglobin drop ≥ 5 g/dL* (provided haemoglobin drop is related to bleed); cardiac tamponade; bleeding requiring surgical intervention for control (excluding dental/nasal/skin/hemorrhoid); bleeding requiring intravenous vasoactive agents

Type 3c: intracranial hemorrhage (does not include microbleeds or hemorrhagic transformation, does include intraspinal); subcategories confirmed by autopsy or imaging or lumbar puncture; intraocular bleed compromising vision

- Type 4: CABG-related bleeding, including perioperative intracranial bleeding within 48 h, reoperation after closure of sternotomy for the purpose of controlling bleeding, transfusion of >5 U whole blood or packed red blood cells within a 48-h period, chest tube output >2L within a 24-h period
- Type 5: fatal bleeding

Type 5a: Probable fatal bleeding; no autopsy or imaging confirmation but clinically suspicious

Type 5b: Definite fatal bleeding; overt bleeding or autopsy or imaging confirmation

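### The cardiovascular-death definition in section 6.2 is over-inclusive and conflicts with itself, so a fatal surgical bleed can be classed either way in the secondary cause-of-death split

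*Combined protocol and SAP*

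**What the plan says.** All the rules are in section 6.2 (Death) of the combined protocol and SAP.

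- **Main use of death.** "All-cause mortality will be considered for the primary analysis", so cause plays no part there.
- **Secondary use.** "For the secondary analysis, death will be classified in two primary categories", namely cardiovascular and non-cardiovascular.
- **Core of the cardiovascular class.** "Cardiovascular death is defined as death due to atherosclerotic coronary heart disease, cerebrovascular accident or (complication of) peripheral embolization".
- **List attached to that core.** The same sentence adds deaths from acute MI and then "stroke, sudden death, non-sudden death, unwitnessed death, and procedure-related deaths".
- **Remainder.** "Non cardiovascular death includes deaths due to all other causes".
- **Presumption.** A death counts as cardiovascular unless a non-cardiovascular cause is clearly demonstrated, "with the exception of death without any additional information, which will be classified as unknown cause of death".

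Section 6.4 defines fatal bleeding separately ("Type 5: fatal bleeding"). Section 4.4.1 admits only patients having a surgical or operative endoscopic procedure.

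**The concern.** The list is wider than the definition it is attached to. The core names three vascular causes, whereas the list names modes and settings of death (sudden, non-sudden, unwitnessed, procedure-related) without tying them to a cardiac or vascular cause. In a registry of operated patients, deaths from surgical complications are among those to be classified, and these are the deaths on which the wording is unclear.

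The background section frames the clinical question as a trade-off between ischaemia when therapy is withheld and bleeding when it is continued, and the secondary objective in 3.2 covers both kinds of event. The split in 6.2 is the only place where the plan separates deaths into cardiovascular and non-cardiovascular. If fatal bleeds can fall on the cardiovascular side, that split cannot be read as thrombotic death against other death.

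**Working it through.** No arithmetic applies: no sample size, power or event figure depends on this definition. The check sets the rules of 6.2 side by side and applies them to example deaths.

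**Step 1: non-sudden death.** Sudden and non-sudden together exhaust all deaths. Taken at its words, the list leaves nothing for the residual class. Read under the three-cause core, it means non-sudden death of coronary, cerebrovascular or embolic origin. The text does not say which reading is meant.

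**Step 2: procedure-related death.** Section 6.2 does not define the procedure. Sections 4.4.1, 4.5.4 and 6.1 use the word for the index operation. The myocardial infarction definition in section 6 mentions a procedure and an operation as alternatives, so a narrower meaning, such as a coronary intervention, is possible. On the first meaning, death from haemorrhage at the index operation is on the cardiovascular list.

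**Step 3: does the override resolve it?** The override needs a clearly shown non-cardiovascular cause. Non-cardiovascular is itself defined as whatever is left after the cardiovascular class. If procedure-related death is inside that class, a fatal surgical bleed is not among the other causes, and the override does not clearly reach it. If the list is read under the core, the override does reach it. The result depends on which sentence is given priority.

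**Step 4: example deaths.**

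| Death | By the list | By the override or exception | Settled? |
|---|---|---|---|
| Acute MI after surgery | Cardiovascular | Not triggered | Yes |
| Documented fatal surgical bleed | Cardiovascular, if procedure means the index operation | Non-cardiovascular, if the cause is accepted as clearly shown | No |
| Documented sepsis after bowel surgery | Cardiovascular, if read as procedure-related or as non-sudden | Non-cardiovascular; the cause is clearly shown | Largely, through the override |
| Unwitnessed, no other information | Cardiovascular | Unknown, by express exception | Largely; the exception is the more specific rule |

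**Step 5: where the split is used.** The primary endpoint in 4.2 contains no death component. The composites in 4.3 name death without a cause, no endpoint there is cardiovascular death, and 7.2 specifies no model for it. BARC type 5 lies inside both bleeding thresholds (grade 3 or higher and grade 4 or higher), so a fatal bleed is recorded whatever label 6.2 gives it.

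**Step 6: size.** The misclassified share would be p × q, where p is the proportion of deaths from bleeding or other non-cardiac surgical causes and q is the proportion of those that adjudicators class by the list and not by the override. The documents give neither p nor q, so the product is not bounded more tightly than 0 to p.

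**The case against.** The best defence reads 6.2 as a whole. The listed items follow a sentence that names three vascular causes, so they can be taken as presentations of those causes. A reading that empties the residual class and makes the override pointless is not the natural one. The override is express, and the committee in 11.2 adjudicates from source documents. Deaths without information have their own exception. Cardiovascular death is not a listed endpoint, and the trade-off is also addressed by separate ischaemic and bleeding endpoints.

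Much of this stands. A reader might infer from the list that almost every death in the registry, or every procedure-related death, must be classed as cardiovascular. The documents do not support that: the word *all* is not attached to procedure-related deaths, having had a procedure does not make a death procedure-related, a documented septic death can be non-cardiovascular under the override, and no figure on causes of death is given. A reader might also see a firm contradiction over unwitnessed deaths; the express exception largely settles it, although 6.2 announces two categories and then uses a third.

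What the defence does not remove is the fatal surgical bleed. It relies on reading a cardiac limit into *non-sudden* and *procedure-related* that the text does not contain, and on an override whose target class is defined by what the list leaves over. BARC type 5 identifies fatal bleeds but is pooled with lesser grades in the bleeding endpoints, and it does not identify other surgical deaths.

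**Conclusion.** The point holds in a limited form. Section 6.2 is over-inclusive and inconsistent with itself: the list can make a fatal surgical bleed cardiovascular, and the override in the same section can make it non-cardiovascular. This is a stated rule that can misclassify deaths, not merely a missing detail.

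The effect is confined to the secondary cardiovascular versus non-cardiovascular split. The primary endpoint, the composites with death from any cause and the BARC type 5 record are unaffected. The share of deaths affected cannot be computed from the documents, and a claim that it approaches all deaths would be unsupported.

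Two assumptions are made. First, *procedure* can include the index operation, as most of the protocol's usage suggests. Second, the NACE and MACE outcomes that 7.2 names without defining use death from any cause, as the composites in 4.3 do. If either used cardiovascular death, the effect would reach further.

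**What to change.** Amend 6.2 before any death is adjudicated, since reclassifying deaths once results are known invites bias:

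1. Limit *non-sudden death* to non-sudden cardiac death.
2. Limit *procedure-related* to deaths from a cardiac or vascular (coronary, cerebrovascular or embolic) complication of the procedure.
3. State that fatal bleeding (BARC type 5) and other non-cardiac surgical deaths are non-cardiovascular. Say explicitly where a fatal intracranial haemorrhage goes, because it could meet both the cerebrovascular core and BARC type 5.
4. Name three categories (cardiovascular, non-cardiovascular, unknown) and class an unwitnessed death without further information as unknown.

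The cost is a rewording of 6.2 and a matching edit to the adjudication form. No new data are needed and the sample size does not change. The downside is that fewer deaths will be classed as cardiovascular, so that category will be smaller and estimated less precisely.

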6.3 Myocardial Infarction

All definite MIs will be counted as events whether they occurred spontaneously or as the direct consequences of a procedure or operation.

The definition of perioperative MI includes cardiac marker evidence of MI with either troponin or CK-MB elevation greater than the ULN with a typical rise and fall⁴⁴ and 1 or more of the following defining features⁴⁵:

- ischemic symptoms (such as chest, epigastric, arm, wrist, or jaw discomfort or shortness of breath),
- development of pathologic Q waves in 2 contiguous leads during ECG,
- ischemic changes detected with ECG (new or presumed-new ST-segment elevation or depression or T-wave inversion in at least 2 contiguous leads during ECG),
- coronary artery intervention (such as percutaneous coronary intervention or coronary artery bypass graft surgery),
- or evidence of MI on cardiac imaging (a new or presumed-new cardiac wall-motion abnormality on echocardiographic imaging or a new or presumed-new fixed defect on radionuclide imaging).
- a patient's autopsy findings demonstrated acute MI.

According to the 3rd Universal Definition of MI⁴⁴,

- following PCI, CK-MB elevation must be $>5 \times$ ULN.
- Following CABG, the definition for an MI requires that cardiac markers are $>10 \times$ ULN.

Outcome adjudicators evaluated all potential MIs, and their decisions will be used in the statistical analyses. The event adjudication committee should also consider the clinical features (eg, renal insufficiency), possible alternative diagnoses (eg, pericarditis), pattern of marker release (eg, absence of a rise and fall), and known sensitivity/specificity of the various cardiac markers in the adjudication of infarction, particularly when there is discordance in the results of multiple markers.

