4. STUDY DESIGN

4.1 Summary of Study Design

The SAS registry will include any patient with previous coronary stenting undergoing any type of surgery or operative endoscopic/endovascular procedure at the participating Centers. Centers will be divided into two groups: Centers that routinely follow the recommendations of the SAS 2 Document and Centers that do not. The relevant clinical, procedural and outcome data (within index admission and at 30 days) will be entered in a specifically designed electronic case record form (eCRF).

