4.4 Participants

4.4.1 Inclusion Criteria

Eligible will be male and female patients > 18 years of age.

Eligible will be patients with previous coronary stenting undergoing any kind of surgical or operative endoscopic procedure at the participating Centers, irrespective of the distance in time between stenting and surgery.

Both candidates to elective and urgent/emergent surgical procedures will be included in the MONET registry.

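### No time zero for outcome events: an MI that leads to urgent surgery, and in a narrower group a presenting bleed, can be counted as a secondary outcome

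*Combined protocol and SAP*

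**What the plan says.** - **Who enters.** Section 4.4.1: "Both candidates to elective and urgent/emergent surgical procedures will be included in the MONET registry". Section 4.4.2 excludes patients who cannot or will not consent, and those with active bleeding that requires stopping an antiplatelet drug. It states that nothing else excludes, so acute MI does not.
- **When outcomes are captured.** Section 4.1: "The relevant clinical, procedural and outcome data (within index admission and at 30 days" go into the eCRF. Appendix A likewise has MACCE and bleeding reported for the index admission. Section 7.2 models in-hospital NACE, 30-day MACE and 30-day BARC bleeding.
- **What counts as MI.** Section 6.3: "All definite MIs will be counted as events whether they occurred spontaneously or as the direct consequences of a procedure or operation". A perioperative MI needs a marker above the ULN with a rise and fall, plus one feature from a list that includes "coronary artery intervention (such as percutaneous coronary intervention or coronary artery bypass graft surgery". "Following CABG, the definition for an MI requires that cardiac markers are" more than 10 times the ULN.
- **What counts as bleeding.** Section 6.4: "All bleeding events will be considered in patients undergoing cardiac and non cardiac surgery". BARC type 3b includes "bleeding requiring surgical intervention for control (excluding dental/nasal/skin/hemorrhoid", and type 3c includes intracranial haemorrhage. Section 4.3 counts grade 3 or higher in non-cardiac surgery and grade 4 or higher in cardiac surgery. Section 7.2 assigns the two thresholds the other way round.
- **What adjudicators are told.** "The event adjudication committee should also consider the clinical features (eg, renal insufficiency), possible alternative diagnoses (eg, pericarditis", together with the pattern of marker release and marker sensitivity and specificity. Events already present before surgery are not mentioned.
- **What is recorded at baseline.** Section 4.5.3 lists prior MI without a date. It lists no item for an MI or a bleed present on admission.

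**The concern.** An event that caused the operation precedes most or all of the perioperative management being compared, and that management cannot change it. If it is counted, two things follow. Where presenting events are equally common in both groups, they add the same events to each side and pull any real difference towards the null. Where they differ, they create a difference that has nothing to do with the SAS 2 recommendations.

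The second case is plausible because section 4.1 forms the groups by centre, and centres can differ in emergency case mix. The propensity model in section 7.2 can correct for this only if it has a variable for the presenting condition, and none is listed.

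**Working it through.** **Does the text let a presenting MI count?** Take a stented patient admitted with MI who goes to urgent CABG.

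1. Eligible: yes (4.4.1), and not excluded (4.4.2).
2. Inside the capture window: yes, because the index admission includes the stay before surgery (4.1, Appendix A).
3. Marker criterion: met by the presenting MI.
4. Qualifying feature: met by symptoms or ECG change, and also by the CABG itself, which is on the list.
5. Stopped by the tenfold post-CABG threshold: no. That threshold governs MI after CABG, not before it. It also sets no condition on the pre-operative value, so markers already high before surgery can help to satisfy it.
6. Stopped by the adjudication guidance: not by any written instruction.

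**Does the text let a presenting bleed count?** Only if all of these hold:

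1. The bleed did not require stopping an antiplatelet drug, or the patient was taking none (4.4.2). The second case can arise because 4.4.1 sets no limit on the time since stenting.
2. The bleed meets BARC type 3, for example through surgery to control it (3b).
3. The patient is in the stratum where type 3 counts: non-cardiac surgery under 4.3, cardiac surgery under 7.2.

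**Size.** The documents give no event rates and no urgent/emergent share, so every rate below is an assumption. Section 7.1 gives 1623 patients, 80% power, 5% significance and a 1:2 ratio, but no rates or effect size. The 1623 therefore cannot be reproduced, and this point does not depend on it.

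Let p be the true post-entry event rate and q the share entering with a qualifying event. Each patient counts once, and the two are taken as independent. Counted rate = q + (1 − q)p.

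*Unequal prevalence, no true effect* (q = 2% in group 1, 4% in group 2):

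- p = 8%: group 1 is 0.02 + 0.98 × 0.08 = 0.0984; group 2 is 0.04 + 0.96 × 0.08 = 0.1168. Ratio 0.1168/0.0984 = 1.19. Presenting events are 0.02/0.0984 = 20% and 0.04/0.1168 = 34% of those counted.
- p = 5%: 0.069 and 0.088. Ratio 1.28.

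*Equal prevalence, no true effect:* both groups have the same counted rate, so the ratio is 1.00.

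*Equal prevalence, true rates 6% vs 10%.* I assume 1623 is split 1:2 into 541 and 1082 (1623/3 = 541). OR = [a/(1 − a)]/[b/(1 − b)] for counted rates a and b. Power is for the two-sided 5% test of two proportions with pooled variance under the null:

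| q in both groups | Counted rates | OR | Power |
|---|---|---|---|
| 0% | 6.0% vs 10.0% | 0.57 | 79% |
| 2% | 7.9% vs 11.8% | 0.64 | 69% |
| 5% | 10.7% vs 14.5% | 0.71 | 57% |
| 10% | 15.4% vs 19.0% | 0.78 | 43% |

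All of these figures are unadjusted.

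**The case against.** The strongest reply is that events after entry were plainly meant. The counting sentence in 6.3 is about mechanism, spontaneous or procedural, and not about timing. The definition that follows it is of perioperative MI. Section 4.5.4 times the follow-up contact from surgery, prior MI is a baseline item, and adjudicators see source documents and weigh the marker pattern. This stands as evidence of intent. A reader might infer from the wording that the plan sets out to count presenting MIs, and the documents do not support that: they fail to rule it out. But intent is not a rule. The 30-day anchor fixes the end of the window and not its start, and different adjudicators or sites could apply different unwritten conventions.

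A reader might also infer that any patient operated on for bleeding enters with an event. That is too broad. The exclusion in 4.4.2 is aimed at such patients, and type 3 bleeding counts in only one stratum. The consent requirement may thin the emergent group further.

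Finally, 1.19 and 1.28 come wholly from assuming twice the prevalence in group 2, before the planned matching. That is correct. They illustrate a mechanism and do not estimate the bias in this registry.

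**Conclusion.** For MI the gap is real: applied as written, the counting rule admits the MI that led to surgery. It affects the secondary ischaemic and net composites, the in-hospital NACE model and, through the same MI definition, the 30-day MACE model. For bleeding it is confined to the patients described above, and how far it reaches depends on how sections 4.3 and 7.2 are reconciled.

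A reader might infer that the main result is at risk. It is not: section 4.2 defines the primary endpoint as antiplatelet discontinuation, which no presenting MI or bleed enters.

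The size cannot be determined from the documents. The direction of any false difference depends on which group has more presenting events. With equal prevalence and equal true rates there is none, but a true effect is diluted. The change is worth making because the exposed endpoints carry the clinical comparison and the remedy is cheap.

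**What to change.** - **Time zero and distinctness.** State in 6.3, in 6.4 and in the adjudication instructions that an event counts only if its onset is after enrolment (or another stated time zero) and it is distinct from the condition that led to the index procedure. Counting from enrolment keeps events that occur during pre-operative drug withdrawal.
- **Raised pre-operative markers.** Require a new rise, judged against the routinely available pre-operative value, plus a new qualifying feature other than the index CABG itself. No added testing is needed, in keeping with section 4.5.3.
- **Data.** Add presenting MI, presenting bleed and event onset date and time to the eCRF. Include the presenting conditions in the propensity model.
- **Thresholds.** Reconcile the BARC grades by type of surgery in 4.3 and 7.2.

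The cost is protocol and adjudication wording, a few eCRF fields and slightly lower event counts. Some presenting-MI cases will remain unclassifiable where routine pre-operative markers are lacking; their number should be reported.

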4.3 Secondary endpoints

Patients undergoing non cardiac surgery:

- The composite of death, myocardial infarction, probable/definite stent thrombosis according the Academic Research Consortium definition⁴⁴ and bleeding events of Bleeding Academic Research Consortium (BARC) grade ≥ 3 at 30 days
- The composite of death, myocardial infarction and probable/definite stent at 30 days
- The incidence of bleeding events of Bleeding Academic Research Consortium (BARC) grade ≥ 3 at 30 days
- The type and the length of discontinuation of any antiplatelet therapy in patients undergoing non cardiac surgery according to time from PCI to surgery
- Rate of non cardiac surgical procedures within 12 months from PCI divided into quartiles (0-3, 3-6, 6-9, 9-12 months)
- Delay in performing non cardiac surgical procedure

Patients undergoing cardiac surgery:

- The composite of death, myocardial infarction, probable/definite stent thrombosis according the Academic Research Consortium definition⁴⁴ and bleeding events of Bleeding Academic Research Consortium (BARC) grade ≥ 4 at 30 days
- The composite of death, myocardial infarction and probable/definite stent at 30 days
- The incidence of bleeding events of Bleeding Academic Research Consortium (BARC) grade ≥ 4 at 30 days
- The type and the length of discontinuation of any antiplatelet therapy in patients undergoing cardiac surgery according to time from PCI to surgery
- Rate of cardiac surgical procedures within 12 months from PCI divided into quartiles (0-3, 3-6, 6-9, 9-12 months)
- Delay in performing cardiac surgical procedure

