4.5.3 In-hospital assessments

The MONET registry does not imply any assessments additional to routine treatment. The following clinical and laboratory variables will be captured by the eCRF:

Clinical characteristics

- Age, gender, body weight.
- Selected coronary risk factors, such as diabetic status, smoking, hypertension, dyslipidemia.

- Cardiovascular status: prior MI, PCI (date of latest stenting), CABG, heart failure, atrial fibrillation, latest left ventricular ejection fraction.

Laboratory tests

- Baseline serum creatinine (eGFR will be automatically calculated by the eCRF using the Cockcroft-Gault formula) and peak serum creatinine during hospital stay.
- Baseline haemoglobin/haematocrit and nadir values during hospital stay.
- CKMB and troponin values should be checked at 6-hour intervals for 24 hours after any suspect ischemic symptoms and/or ischemic ECG changes in the perioperative period, unless otherwise recommended by local practice. The peak value of CKMB will be recorded in the eCRF.

Electrocardiogram

A standard 12-lead ECG will be taken preoperatively, in the case of ischemic symptoms and at discharge.

Concomitant Medications

The following medications will be captured by the eCRF:

- Aspirin
- P2Y₁₂ inhibitors (further subdivided as ticlopidine, clopidogrel, prasugrel, ticagrelor)
- Betablockers
- Statins
- ACEI, ARBS
- Oral anticoagulants (warfarin, acenocumarol, apixaban, dabigatran, edoxaban, rivaroxaban)

- Low-molecular weight heparin
- Tirofiban or eptifibatide
- Cangrelor

The dates and times of perioperative discontinuation and reinstitution (if any) will also be captured.

Drug therapy at discharge and at the 30-day contact will be captured by the eCRF.

Index PCI and surgical procedure details

Details of PCI and surgical procedures will be obtained from interrogation of the medical records and hospital charts.

The delay from stenting to surgery and the type of stent (BMS, first or second generation DES), stent number, length and diameter will be recorded. Surgeries will risk-stratified according to the American College of Cardiology/American Heart Association classification [11]. Moreover, the American Society of Anaesthesiologists (ASA) physical status will be assessed for each patient [21].

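### As the MI definition is written, an index CABG satisfies its own supporting-feature requirement, so an isolated marker rise and fall above 10 x ULN meets the definition in those patients

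*Combined protocol and SAP*

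**What the plan says.** Section 6.3 (Myocardial Infarction) builds perioperative MI from two parts. The first is "cardiac marker evidence of MI with either troponin or CK-MB elevation greater than the ULN with a typical rise and fall". The second is "1 or more of the following defining features". Six features follow: ischaemic symptoms, new Q waves, ischaemic ECG changes, a coronary intervention, imaging evidence and autopsy evidence. The fourth reads "coronary artery intervention (such as percutaneous coronary intervention or coronary artery bypass graft surgery").

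The same section adds a threshold for CABG patients: "Following CABG, the definition for an MI requires that cardiac markers are" more than 10 times the ULN. It also says "All definite MIs will be counted as events whether they occurred spontaneously or as the direct consequences of a procedure or operation". Adjudicators evaluate every potential MI, and their decisions enter the analysis.

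Index CABG patients are in the study. Section 4.4.1 states "Eligible will be patients with previous coronary stenting undergoing any kind of surgical or operative endoscopic procedure at the participating Centers", and admits elective and urgent or emergent cases alike. Section 4.3 has a separate block headed "Patients undergoing cardiac surgery", and MI is a component of both composites there. Section 6.4 includes CABG-related bleeding (BARC type 4). No separate MI definition is given for cardiac surgery.

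Under section 4.5.3, CK-MB and troponin are drawn after suspected ischaemic symptoms or ECG changes, "unless otherwise recommended by local practice".

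**The concern.** After non-cardiac surgery the intervention feature makes sense: a patient who needs PCI or CABG in the days after a hernia repair probably had an ischaemic event. When CABG is the index operation, the same words describe the reason for enrolment and carry no information about a new infarct. A requirement meant to separate infarction from marker release alone then no longer does so.

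At stake is what MI means in the cardiac-surgery composites. An isolated rise can be seen only if someone draws the markers, and under the protocol's default someone does so only when symptoms or ECG changes prompt it. Such rises would therefore surface mainly where local practice is to sample routinely. Section 4.1 forms the groups by centre. Section 7.2 then drops patients at consensus-document centres who were not managed by the document, which ties exposure still more closely to centre. Propensity matching on patient covariates would not by itself remove a centre-level difference in detection.

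Timing is also left open. Section 4.5.3 names baseline creatinine and haemoglobin but no baseline cardiac marker, and of the marker values it specifies only peak CK-MB for the eCRF. The definition does not say that the rise must begin after the operation starts. For a patient taken urgently to CABG with markers already raised, telling the presenting infarct from a new one depends on whatever records reach the adjudicators.

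**Working it through.** The plan states no MI rate, CABG share or marker distribution, so there is no figure of its own to reproduce. The check is on the logic of the definition.

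**Rule for an index-CABG patient (section 6.3, Myocardial Infarction).** MI = (marker > 10 x ULN) AND (typical rise and fall) AND (at least 1 of 6 features).

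**Patient with none of the other five features** (no symptoms, Q waves, ECG change, imaging or autopsy evidence):

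| Marker | Rise and fall | Index CABG counts as the feature | Index CABG excluded |
|---|---|---|---|
| 5 x ULN | no | not MI | not MI |
| 5 x ULN | yes | not MI | not MI |
| 11 x ULN | no | not MI | not MI |
| 11 x ULN | yes | **MI** | **not MI** |

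**All feature combinations.** The other five features give 2^5 = 32 combinations. Take a marker of 11 x ULN with rise and fall.
- Index CABG counted: all 32 qualify, so the feature requirement excludes nobody.
- Index CABG excluded: 31 qualify. The one that changes is the combination with no other feature, that is, the isolated marker rise.

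**How this reaches the endpoint.** Let t be the proportion of index-CABG patients with a feature-supported MI, s the proportion with an isolated rise and fall above 10 x ULN, p the share of the latter who are sampled, and a the share of those that adjudicators accept. Then:
- counted MI rate = t + p·a·s
- inflation = (t + p·a·s) / t
- spurious difference between groups with the same t, a and s = a·s·(p1 − p2)

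The last line is zero if both groups sample alike (p1 = p2) or if adjudicators reject every isolated rise (a = 0). The documents give none of t, s, p or a.

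**Illustration on assumed values only.** Take t = 3–5% and s = 2–20%, neither from the documents.
- Upper limit, every rise detected and accepted (p = a = 1): inflation runs from (5 + 2)/5 = 1.4 to (3 + 20)/3 = 7.7.
- Lower limit, every isolated rise rejected (a = 0): inflation is 1.

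The spread shows that the result depends on inputs the plan does not fix. It is not an estimate.

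**The case against.** **The adjudicators decide.** This stands in part. Section 6.3 makes their decisions final for analysis and asks them to weigh clinical features, alternative diagnoses, the pattern of marker release and marker accuracy. Section 11.2 gives them source documents and films. A reader might infer that every isolated rise above the threshold automatically becomes an MI, and the documents do not support that. But nothing tells adjudicators to set the index CABG aside or to require another feature. A committee applying the list faithfully would accept the case, and one using judgement might not.

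**The natural reading is an intervention prompted by the event.** The other five features are all evidence of infarction, so this is probably the intent. The text does not say it.

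**The CABG clause invokes the Third Universal Definition, which may carry further conditions.** The protocol restates only the marker threshold, and the source cannot be checked from these documents. If it does require supporting evidence, the protocol's own list still lets the index CABG supply it.

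**On the default pathway little changes.** This stands. A patient sampled because of symptoms or ECG changes will usually already have one of those features. The defect matters mainly where markers are drawn routinely.

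**The dependence on centre sampling comes from section 4.5.3.** This also stands. Rewording 6.3 would remove the isolated-rise part of it, not all of it. No passage links routine sampling to use of the consensus document, so an imbalance between groups is possible but not shown.

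**Records can already be uploaded.** Section 4.6 provides for laboratory records to be uploaded when adjudication requires them. That covers existing preoperative marker values, so no new upload rule is needed.

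**Conclusion.** The point holds as a narrow defect of wording. For index-CABG patients the supporting-feature requirement excludes nobody, and an isolated marker rise and fall above 10 x ULN meets the written definition. This rests on taking the list literally and on reading the CABG threshold as the only added condition, which is all the protocol states.

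Three stronger readings are not supported:
- That every index-CABG patient already meets the MI definition. Only the feature requirement is met by enrolment; the threshold and the rise and fall are still needed, so a single high value is not enough.
- That the resulting excess would outweigh any real difference between strategies. The documents give no rate, CABG share or effect size for MI, and the inflation in the working ranges from none to several-fold on assumed inputs.
- That the primary endpoint is affected. The second section numbered 6.3 (Stent thrombosis) places MI in an adjudication order for the primary endpoint, but section 4.2 defines that endpoint as antiplatelet discontinuation, with no clinical event in it. The sample size is likewise untouched.

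The effect is confined to MI-containing secondary outcomes in the CABG subset of the cardiac-surgery stratum, whose size is not stated. Whether it biases the group comparison depends on sampling practice by centre, which is unknown.

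**What to change.** In section 6.3 (Myocardial Infarction) and in the adjudication instructions, state that:
- the index operation does not count as the coronary-intervention feature; only a later coronary intervention performed for suspected ischaemia does;
- MI after index CABG needs the stated criterion of more than 10 x ULN with rise and fall, plus at least one other listed feature;
- onset must be after the start of the index operation. Where a preoperative marker value exists, adjudicators can judge this from records uploaded under section 4.6.

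The cost is a short text change. It needs no new tests or visits and changes only how events are classified. The downside is fewer adjudicated MIs in the CABG subset, and so fewer events in those composites. The change does not make marker sampling uniform across centres, so the report should still note that MI ascertainment may vary with local practice.
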